**REVISION HISTORY**

**\*This table should only be used during submission of a Modification application to the IRB.**

Revision #	Version Date	Summary of Changes	Consent Change?
2	01/23/2022	
 
• Data sharing agreement added, complying with the NIH requirement (Section 16.). Parent consent form has been updated to include this data sharing details. This does not impact the EI providers' consent.
 
• Recruitment email address change on recruitment letters.
 
• Height and weight measurement procedure and exit interview guides have been modified to improve clarity.
 
	Yes
3	09/21/2022	
 
• Eligibility criteria for the parent-child dyads has been updated
 
• The timing of asking the autism spectrum disorder (ASD) diagnosis or at risk/monitored for ASD status has been updated by adding another time point at the 5-month follow-up assessment
 
• The health conditions questionnaire timing has been updated to add “T3” – follow-up time point (Table 4. in Section 5.7). A short self-report questionnaire with the same 4 items on health conditions/medications
 
	Yes

		
assessed at baseline through the demographic questionnaire will be used
 
 
• Consent forms have been updated to reflect the eligibility criteria and the timing of asking the ASD diagnosis or at risk/monitored for ASD status
 
• A new recruitment flyer is added for the Early Steps to use on their Facebook page
 
• ClinicalTrials.gov registration number has been updated
 
	
--	--	--------------------------------------------------------------------------------------------------------------------------------------------------------------------------------------------------------------------------------------------------------------------------------------------------------------------------------------------------------------------------------------------------------------------------------------------------------	--

## 1.0 Study Summary

Study Title	An integrated nutrition intervention through the Part C Early Intervention Services to promote healthy eating habits for children with ASD
Study Design	Randomized controlled trial
Primary Objective/Purpose	Aim 1: To refine the Autism Eats manual and intervention materials. Aim 2: To evaluate the feasibility and preliminary efficacy of Autism Eats in improving dietary intake and mealtime behaviors of children with ASD.
Secondary Objective(s)/Purposes	To explore whether child weight status differs between Autism Eats and enhanced usual care groups at 5-month follow-up assessment.
Research Intervention(s)	Autism Eats – Early childhood nutrition intervention
ClinicalTrials.gov NCT #	NCT05194345
Study Population	Early intervention providers and parent-child dyads (child aged 0-36 months clinically diagnosed with ASD)
Sample Size	146 individuals Aim 1: 10 EI providers, 10 parents Aim 2: 30 EI providers, 48 parent-child dyads (48 parents and 48 children)
Study Duration for individual subjects	Aim 1: up to 3 hours per participant to review manual and provide feedback. Aim 2: Parent-child dyads : The Autism Eats intervention group will spend about 8.5 hours over 5 months (baseline, post intervention, and 5-month follow-up assessments are 30 minutes each, 25-30 minutes weekly sessions for up to 10 weeks, two 25-30 minutes monthly booster sessions, and a 60-minute exit interview), and the We Can! EUC control group will spend about 3 hours over 5 months (baseline, post intervention, and 5-month follow-up assessments are 30 minutes each, one 25-30 minute nutrition session, and a 60-minute exit interview). EI provider : The Autism Eats intervention group EI provider will spend about 12 hours over 5 months (two 90-minutes training sessions, 25-30 minutes weekly sessions for up to 10 weeks, two 25-30 minutes monthly booster sessions, 10-minute fidelity checklist completion

	after each session, and a 60-minute exit interview), and the We Can! EUC control group EI provider will spend about 4.5 hours over 5 months (two 90-minutes training sessions, one 25-30 minutes session, 1-2-minute written material distribution at their 9 weekly EI sessions, and a 60-minute exit interview).
Study Specific Abbreviations/ Definitions	EI=Early Intervention; EUC=Enhanced Usual Care; ASD=Autism Spectrum Disorder; BAMBI=Brief Autism Mealtime Behavior Inventory; IDEA=Individuals with Disabilities Education Act

## 2.0 Objectives

2.1 There is an unmet need for nutrition interventions that address both autism spectrum disorder (ASD) specific feeding challenges and unbalanced eating habits among children with ASD to prevent future chronic health conditions. Children with ASD tend to consume few fruits and vegetables and mainly high-energy dense foods, including sugar-sweetened beverages and processed snacks. Obesity prevalence in children with ASD is up to 40% higher than in typically developing children, and recent studies show significantly elevated risks of hyperlipidemia and hypertension among individuals with ASD, regardless of using psychotropic medications. Considering the increased risks for diet-related diseases and the fact that many children with ASD develop various feeding problems such as selective eating patterns and food refusal, a novel intervention approach that addresses both ASD-specific feeding challenges and healthy eating development is urgently needed to prevent serious feeding problems and reduce chronic disease risks. Our interdisciplinary team conducted a preliminary study to examine diet quality and mealtime behaviors among diverse children with ASD in Florida (34% Hispanic/Latino) and parental preferences for nutrition interventions. Based on the study findings, we developed the manual for our nutrition intervention, Autism Eats, for children with ASD enrolled in the Part C of Individuals with Disabilities Education Act (IDEA) Early Intervention (EI) services. Our Autism Eats manual and parent materials are based on ASD-specific feeding strategies such as escape extinction and food chaining combined with behaviorally-focused nutrition intervention strategies such as goal setting and weekly meal planning to promote healthy eating. We pilot-tested the intervention with a small number of EI providers and parent-child dyads (n=5) to examine how intervention components fit with the Part C service setting. Preliminary fidelity and provider interview data indicated that the intervention manual was easy to follow and has potential to be widely implemented in the EI services, indicating a good fit. Herein, our goal is to refine our intervention materials and conduct a pilot RCT to test the feasibility and preliminary efficacy of this innovative nutrition intervention program, Autism Eats, to prevent problematic mealtime behaviors and promote development of healthy eating habits among children with ASD enrolled in Part C EI services in Florida. The Specific Aims are:

Aim 1. To refine the Autism Eats manual and intervention materials.

Aim 2. To evaluate the feasibility and preliminary efficacy of Autism Eats in improving dietary intake and mealtime behaviors of children with ASD.

2a. Test the feasibility of enrollment, implementation, and evaluation of Autism Eats.

2b. Assess the preliminary efficacy of Autism Eats for improving child dietary intake and mealtime behaviors.

Exploratory Aim. To explore whether child weight status differs between Autism Eats and EUC groups at 5-month follow-up assessment.

2.2 Hypothesis 1: We hypothesize that Autism Eats will be feasible and well-received by EI providers and parent-child dyads.

Hypothesis 2: We hypothesize that there will be differences in children dietary food intakes, variety, diet quality, and mealtime behaviors between children who participate in Autism Eats and those in the EUC groups at post-intervention and 5-month follow-up from baseline.

### **3.0 Background**

3.1 The prevalence of ASD has increased drastically in recent years, with current estimates at 1 in every 54 (more than 2 million) children affected in the United States, which is approximately 10% higher than the estimate in 2014 and 175% or 2.8 times higher than the first estimates reported in 2000. In addition, Florida has the highest prevalence of ASD (4.88% compared to 2.9%, the national average). Without intervention, individuals with ASD are at significant risk for developing diabetes, coronary heart disease, and cancer by midlife.

Unhealthy food choices in children with ASD are a growing concern with potential for lifelong impact. Children with ASD tend to consume few fruits and vegetables and excess calories from high-energy dense foods, including starches, sugar-sweetened beverages, and other highly processed foods and snacks, contributing to increased rates of obesity and other diet-related diseases. ASD-specific problematic mealtime behaviors and food selectivity should be addressed. Prior research reported that children with ASD experience up to 5 times more feeding problems, including problematic mealtime behaviors (e.g., not staying seated and showing aggressive behaviors or tantrums during mealtime) and food selectivity (i.e., only eating a narrow variety of foods), compared to their neurotypical peers, which may increase the risk for developing poor eating behaviors and inadequate nutrient intakes. Lower intakes of protein, calcium, phosphorus, riboflavin, and vitamin B12 have been reported in children with ASD. Due to these feeding problems, parents' attempts to expand their children's diets may be more challenging. Therefore, interventions for this population should address ASD-specific feeding challenges.

Early childhood nutrition interventions have shown promise of improving eating behaviors and slowing weight gain in typically developing children, but their effectiveness is understudied among children with developmental disabilities. Currently, there is no evidence on whether an early childhood nutrition intervention emphasizing both ASD-specific mealtime behaviors and healthy eating behaviors has benefits of mitigating problematic eating behaviors and developing healthy dietary habits for children with ASD. Our study proposes to explore whether early childhood is an optimal time period for starting nutrition intervention and the long-term goals is to examine how dietary risk factors can be managed in early childhood to improve health trajectories in population with ASD.

3.2 We pilot-tested the intervention with a small number of EI providers and parent-child dyads (n=5) to examine how intervention components fit with the Part C service setting. Preliminary fidelity and provider interview data indicated that the intervention manual was easy to follow and has potential to be widely implemented in the EI services, indicating a good fit. Participants further suggested innovative ways to improve the intervention such as adding more hands-on activities, booster sessions, and social media components.

## 4.0 Study Intervention

4.1 Autism Eats intervention (Table 1): Lessons integrate ASD-specific feeding strategies such as escape extinction, food chaining, and making regular mealtime routines and behaviorally-focused nutrition content and activities utilizing goal setting, healthy meal planning, monitoring progress, strategies to overcome barriers, and creating healthy home food environment. The EI providers are well-trained to use personalized intervention and coaching approach in their EI services, which will be applied to Autism Eats activities as well (e.g., using the child's favorite foods for lesson activities). There is no content difference between in-person and telehealth versions of the program, except those instructions for providers are tailored to in-person vs. telehealth settings.

Table 1. Components of *Autism Eats* nutrition intervention

Components	Example Activity
Lessons: topics and objectives	
L1. Feeding Milestones: Understand feeding milestones for infants and toddlers.	Feeding milestone screening
L2. Sensory Properties of Foods: Taste, Flavors, & Textures: Explore the role of senses as it pertains to taste, flavor, and texture in the development of food preferences.	Exploring senses activity
L3. Introducing New Foods: Understand and utilize strategies for introducing new foods into the child's diet.	Repeated exposure
L4. Balanced Eating and Nutrition: Examine the benefits of healthy foods and learn how to integrate them in a daily menu.	Creating a meal plan
L5. Food Allergies, Special Diets, and Supplements:	Food sorting activity

Understand food allergies, special diets, and supplements that may affect or be beneficial for their child.	
L6. Beverages: Identify age-appropriate beverages and examine the benefits of healthy beverage selection.	Family beverage goal setting
L7. Mealtime Routines and Schedules: Establish a mealtime routine and create a consistent eating schedule.	Mealtime routine
L8. Restructuring Food Environment: Develop strategies to make healthy choices and have a pleasant experience while eating outside the home.	Strategies for eating out
L9. Hunger and Fullness Cues: Build confidence in recognizing when the child is hungry or full.	Responding to hunger and satiety
L10. Maintaining Healthy Nutrition: Create long-term strategies to sustaining healthy eating habits.	Restructuring the home food environment
Booster L1. Where are We Now?: Review previous lessons and discuss barriers for healthy eating and ways to overcome them.	Goal reinforcement
Booster L2. Celebrating Achievements Celebrate healthy eating achievements with positive reinforcement.	Positive reinforcement practice
Static website repository Project description and lesson resources	Handouts available online
Social media Private social media (Facebook) group page	Extra motivational resources and parent engagement

L = Lesson

EUC control group materials are from the evidence-based materials that are already developed and available online (in both English and Spanish):

<https://www.nhlbi.nih.gov/health/educational/wecan/index.htm>

[figure not shown]
We will download one handout for each week and email EI providers to distribute for parent-child dyads who are randomly assigned into the EUC group.

## 5.0 Procedures Involved

### 5.1

Aim 1: The EI providers (n=10) and parents (n=10) will be invited to review the intervention manual and materials and provide their feedback. Participants will receive a survey link for the manual review which is described in 5.2 below. Based on the results of the review, all intervention materials will be further refined and finalized.

Aim 2: The protocol for this project is designed to conduct a preliminary RCT. This pilot RCT compares Autism Eats (n=24 parent-child dyads) to the EUC condition using We Can! materials (n=24 parent-child dyads). EI providers (n=30) in two Florida counties (Hillsborough and Polk Counties) will be recruited on a rolling basis and parent-child dyads will be recruited through those EI providers. Baseline assessment will be scheduled. Study participants will be randomized into two intervention groups (Autism Eat and EUC We Can!) after collection of the baseline data. Random assignment will be conducted by [name] (Co-I) utilizing a random number generator. Participants in Autism Eats will receive the intervention components while those in the EUC group receive comparison We Can! materials. Data collection will be performed at three time points. Study design is also described in Figure 1.

5.2

 Audio/Video Recording	 Psychophysiological Recording
 Behavioral Interventions	 Record Review - Educational
 Behavioral Observations and Experimentations	 Record Review - Employee
 Deception	 Record Review- Medical
 Focus Groups	 Record Review - Other
 Interviews	 Specimen Collection or Analysis
 Investigational Device – Non-Significant Risk (e.g. Mobile Applications)	 Surveys and/or Questionnaires
 Psychometric Testing	 Other Social-Behavioral Procedures

**Aim 1:** We will invite EI providers and parents to review the intervention manual and materials and provide their feedback. The review invitation will be sent out through an online survey link (RedCap).

For EI providers, the feasibility scale used in our pilot study will be used. Seven questions will address feasibility of implementing each lesson, clarity of instructions, relevance to the EI services, acceptability by parents, satisfaction of resources/references, and clarity and relevance to the overall goal. Open-ended questions on each lesson will allow EI providers to share recommendation regarding each session's content and materials. The manual review will take up to 3 hours per participant.

For parents, the feasibility scale will be tailored to parent participants and address clarity of instructions, acceptability, satisfaction of intervention materials, and feasibility of implementing feeding practices at home. Open-ended questions on each lesson will allow parents to share recommendation regarding each session's content and materials. The survey will take about 1-2 hours per participant.

**Aim 2:** We will track the number of EI providers and parents reached by the recruitment methods. We will monitor and document reasons for dropping out, and clearly indicate whether it was the provider or the parent who decide to drop out. Completion rates of assessments at all data collection time points, training sessions, and lesson and booster lesson implementation will be tracked and recorded.

Training session materials include a 90-minute presentation prior to the intervention implementation and a 90-minute mid-training session in-between lesson 4 and 8. Both training sessions have been developed and pilot-tested in our preliminary feasibility study, and all enrolled EI providers participated in those sessions without attrition. On-going EI provider support will be provided by offering co-coaching the sessions when the EI providers need assistance on nutrition-specific activities. Randomly selected sessions (20%) will be observed and check whether all lesson components are consistently implemented as designed across EI providers, adapting the 5-point scale from a previous clinical trial. We will examine whether our intervention sessions fit the context of the EI services as well as the needs, expectations, and values of the EI providers, using an exit survey. Using those selected sessions, compatibility of the intervention content and activities for different levels of children's autism features and symptoms will also be examined from the observation or video-recorded sessions. EI providers and parents will be invited for a semi-structured interview at 5-month follow-up. The interviews will be audio/video recorded for transcriptions.

Three-day food record is a gold-standard assessment for dietary intake of individuals. Three 24-hour food records will be completed by parents using the NCI's Automated Self-administered 24-Hour Dietary Recall. Research assistants (RA) will provide guidance as needed. We focus on average daily dietary intakes by food groups (i.e., fruit, vegetables, grain, protein, and dairy) and daily food variety. For all children aged 2 years or older, diet quality will be determined by the Healthy Eating Index's total and sub-component scores (adequacy vs. moderation food categories). The Brief Autism Mealtime Behavior Inventory (BAMBI) will be used to assess children's mealtime behaviors. The BAMBI is a validated assessment tool that contains 18 questions and uses a 5-point Likert scale. A trained RA (single-blinded) will assess children's height and weight with a professional stadiometer and a weight scale following the standardized protocol used in previous studies. As a standard weight status assessment for birth to 36 months, weight-for-length based on the CDC growth chart will be calculated. Parent BMI will be calculated and used as a covariate in data analysis. If height and weight

information is available for the spouse of the participating parent or the other biological father/mother, it will be recorded. Questions on sex, race/ethnicity, family history of ASD, age, parental education, income, insurance status, and history of other illnesses and comorbid health conditions such as epilepsy, sleep disorders, and anxiety disorders will be asked at baseline. We will also administer the Child Feeding Questionnaire, a validated questionnaire used in our multi-site nutrition intervention clinical trial.

5.3 Our comparison group will receive an enhanced usual early intervention service. Enhanced Usual Care (EUC) Comparison. A one-time 25-minute session on nutrition (modified lesson 4 of the Autism Eats) will be embedded in the regular EI services. The EUC EI providers will receive one 30-minute training session on EUC content and activities. To maintain scientific control for attention threats and increase rigor, EUC families will also receive publicly available web-based information on healthy eating using We Can! materials weekly over 10-weeks by email to correspond with the number of Autism Eats sessions. We Can! is evidence-based nutrition and physical activity materials from the National Heart Lung and Blood Institute (<https://www.nhlbi.nih.gov/health/educational/wecan/index.htm>). We will also send out two monthly booster information by email.

5.4 Potential risks are minimal. Participants may experience psychological discomfort during intervention sessions or while answering survey questions or having their height and weight measured. To protect against risk, research procedures will be explained, and any questions will be answered. The risks and benefits of participation will be described before obtaining a signed IRB-approved informed consent from EI providers and parents, respectively. Children younger than 3 year old cannot complete assent form, so parents will sign the consent forms for their children and for themselves. No pressure will be exerted on the subjects to participate, and they have the right to withdraw from the study at any time. Research personnel will be told to report any untoward participant reactions directly to the research project coordinator and the PI. Minor concerns raised by providers and parents (e.g. embarrassment about being weighed) will be addressed by the research staff. Participants will be carefully monitored using the resources of the University of South Florida, a research institution. [name] and [name] each bring extensive experience working with the development and evaluation of behaviorally-focused interventions targeting dietary behaviors to children. The research team will be available to refer any participants to appropriate specialists as necessary. EI providers and parents will be told that they can terminate their participation in the study at any time with no penalty.

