## **8.0 Study Timelines**

8.1 Activities for Aim 1 will start in October 2021 and Aim 2 is planned to be started in January 2022. The project will end in July 2023. Participants will be recruited in a rolling basis. For Aim 2 (RCT), each parent-child dyad will have three data collections: baseline (T1), post-intervention (T2), and 5-months follow-up from baseline (T3). The Enhanced Usual Care (EUC) comparison group will receive one intervention session and periodic written materials from We Can!.

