## **11.0 Local Number of Subjects**

11.1

For Aim 1, 10 EI providers and 10 parents will be enrolled.

For Aim 2, 30 EI providers and 48 parent-child dyads (48 parents and 48 children) will be enrolled.

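### The Protocol plans 48 parent-child dyads and the SAP 30; EUC provider training is also described in two ways, and the unit of allocation is not stated outright

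*Protocol*

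**What the plan says.** **Number of dyads.** Protocol Section 5.1 gives the arm sizes: "This pilot RCT compares Autism Eats (n=24 parent-child dyads) to the EUC condition using We Can! materials (n=24 parent-child dyads". Section 11.1 repeats the total ("For Aim 2, 30 EI providers and 48 parent-child dyads"), and the Study Summary (Section 1.0) gives 146 individuals over both aims. Section 5.1 adds that the dyads are recruited through the enrolled EI providers. The SAP's sample-size paragraph gives N=30 for EI providers and dyads with 1:1 randomization and says that no sample size calculation is needed for a pilot. The Reach/Participation row of SAP Table 3 runs until 30 dyads are recruited.

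**EUC provider training.** Section 1.0 says "the We Can! EUC control group EI provider will spend about 4.5 hours over 5 months (two 90-minutes training sessions", followed by the other EUC tasks. Section 20.2 pays for a first and a second training session in both groups. Section 5.3 says "The EUC EI providers will receive one 30-minute training session on EUC content and activities".

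**Unit of allocation.** Section 5.1 says "Study participants will be randomized into two intervention groups (Autism Eat and EUC We Can!) after collection of the baseline data". The SAP also speaks only of study participants. Section 4.1 is more specific: handouts go out by "email EI providers to distribute for parent-child dyads who are randomly assigned into the EUC group". Section 8.1 attaches the assessments to the dyad: "each parent-child dyad will have three data collections: baseline (T1), post-intervention (T2), and 5-months follow-up from baseline (T3". Providers, however, are described by group in Section 1.0 (for example "The Autism Eats intervention group EI provider will spend about 12 hours over 5 months"), in Section 5.3 and in Section 20.2. The Aim 2b analysis has time and treatment condition as its factors and no provider term.

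**The concern.** The pilot's statistical product is a set of variances, effect sizes and confidence intervals, together with the feasibility benchmarks. The number of dyads fixes the precision of the former and the point at which the latter are judged. A reader holding both documents cannot tell when recruitment is complete or how wide the intervals are meant to be.

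The two accounts of EUC provider training matter because training is part of what defines the comparison condition. Fidelity and provider burden cannot be described consistently while both accounts stand.

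The unit of allocation matters less. Once dyads outnumber providers, some providers have several dyads. The report then needs to say whether a provider could deliver both programmes, and the analysis should match the unit that was actually allocated.

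**Working it through.** **1. The Protocol's own total.** Aim 1 has 10 providers and 10 parents; Aim 2 has 30 providers, 48 parents and 48 children: 10 + 10 + 30 + 48 + 48 = 146, as stated. With 30 dyads it would be 10 + 10 + 30 + 30 + 30 = 110. The Protocol is therefore consistent within itself at 48, and 24 + 24 = 48.

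**2. Precision.** The documents give no SD, so the half-width is in units of the SD of change. Assumptions: equal SDs, complete data, independent dyads, and a t interval as a stand-in for the planned nonparametric one. Half-width = t(0.975, 2n − 2) × √(2/n).
- n = 24 per arm: t(0.975, 46) × √(2/24) = 0.581 SD.
- n = 15 per arm (N=30 at 1:1): t(0.975, 28) × √(2/15) = 0.748 SD.
- Ratio: 0.748 / 0.581 = 1.287, about 29% wider.
- With 20% lost (19.2 and 12 per arm): 0.654 and 0.847 SD.

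**3. Table 3 counts.** The percentages are the same at either size; the counts are not.
- Attrition below 20%: 9/48 = 18.75% passes and 10/48 = 20.8% fails; 5/30 = 16.7% passes and 6/30 = 20% fails. The maximum is 9 against 5 dropouts.
- Reach above 75%: 48/63 = 76.2% passes and 48/64 = 75% fails; 30/39 = 76.9% passes and 30/40 = 75% fails. The maximum is 63 against 39 approached dyads.

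**4. EUC provider hours.** Section 1.0 states about 4.5 hours for training, one session of 25-30 minutes, nine handouts at 1-2 minutes each and a 60-minute interview.
- Two 90-minute trainings: (180 + 25 + 9 + 60)/60 = 4.57 h to (180 + 30 + 18 + 60)/60 = 4.80 h.
- One 30-minute training: (30 + 25 + 9 + 60)/60 = 2.07 h to (30 + 30 + 18 + 60)/60 = 2.30 h.

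The stated figure roughly matches the first description only. That shows the two sections cannot both hold; it does not show which is intended.

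**5. Sharing of providers.** 48/30 = 1.6 dyads per provider, and 48 − 30 = 18 dyads exceed one per provider. At least one provider must serve more than one dyad. At 30 dyads and 30 providers sharing is not forced.

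**6. Whether the hours confine a provider to one arm.** For one Autism Eats dyad, with 12 sessions and 12 checklists: (180 + 12×25 + 12×10 + 60)/60 = 11.0 h to (180 + 12×30 + 12×10 + 60)/60 = 12.0 h, against about 12 stated. A second Autism Eats dyad adds 12×(25 + 10) to 12×(30 + 10) minutes, or 7-8 h, giving 18-20 h, which does not fit. Adding one EUC dyad costs only 25 + 9 = 34 to 30 + 18 = 48 minutes, for a total of 11.6-12.8 h, which still fits. The hours do not exclude a provider with one dyad in each arm.

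**The case against.** Several points can be made for the plan.

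- **The SAP's N=30 can be read as counting providers.** The sentence alone is ambiguous, but Table 3 stops at 30 dyads, so the conflict stands.
- **Neither size is wrong for a pilot without a power claim.** This is correct. The wider interval is a consequence of choosing 30, not a bias. The fault is that two sizes are in force.
- **The Table 3 thresholds are percentages.** This is also correct; only the counts and the stopping point move.
- **Figure 1 is not shown, and the SAP refers to a measures section that is not in the file.** Either could state the unit of allocation, so the claim extends only to the visible text. Neither would remove the 48/30 or the training conflict.

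A reader might go further and infer from the group-specific hours and training that each provider belongs to one arm, so that the trial is clustered and the Aim 2b analysis invalid. The documents do not support this. Those passages describe burden and training by role, no sentence confines a provider to a single arm, and Section 4.1 says that dyads are randomly assigned. A reader might equally infer that shared providers must dilute the effect. That needs a degree of carry-over and a caseload spread that the documents do not give, so no figure for it is offered here.

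**Conclusion.** The sample-size conflict is real and should be fixed: 48 dyads throughout the Protocol, 30 in the SAP. It amounts to half-widths of about 0.58 against 0.75 SD under the assumptions stated, and to different counts behind two feasibility benchmarks. The SAP is dated 10/24/2022, after the last listed Protocol revision (09/21/2022), and no listed revision mentions sample size, so the dates do not settle which number governs.

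The conflict over EUC provider training is also plain on the page.

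The unit of allocation is a minor clarification. The visible text favours the dyad, and sharing is certain only if 48 stands. Nothing visible says whether one provider may deliver both arms, and nothing visible shows that the planned analysis is wrong. No power claim is affected, because the pilot makes none.

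**What to change.** 1. Put one dyad number in Protocol Sections 1.0, 5.1 and 11.1, the SAP sample-size paragraph and SAP Table 3. If 48 stands, correct both SAP places to 48 dyads through 30 providers. If 30 stands, the Protocol's arm sizes and its total of 146 change as well.
2. Reconcile the descriptions of EUC provider training in Protocol Sections 1.0, 5.3 and 20.2.
3. State the unit of allocation in one sentence in Section 5.1 and in the SAP. Record the provider ID for each dyad in the existing tracking log, and report how many providers delivered both arms.
4. Account for provider in the Aim 2b intervals only if providers were allocated to a single arm.

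The cost is a few sentences and one log field, with no extra visits or staff and no change to allocations already made. If step 4 applies, it adds a resampling step or a model term, and the provider variance would be poorly estimated at 1.6 dyads per provider.
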